6.1.9.4 Buffy Coat

Blood samples will be collected in one EDTA purple top tube (approximately 10 ml) prior to study treatment at screening (may be collected at the same time as blood drawn for routine laboratory tests).

Samples should be processed the day of collection according to the buffy coat isolation protocol in the Laboratory Manual.

Samples should be stored at -80°C.

6.1.9.5 Serum Cytokines

Blood samples will be collected in one yellow-gold top serum separation tube (approximately 5 mL) prior to study treatment at screening (may be collected at the same time as blood drawn for routine laboratory tests) and at the time of surgery.

Samples should be processed the day of collection according to the instructions provided below:

1. Fill tube completely. Invert 5-6 times and stand upright for a minimum of 30 minutes to clot.
2. Centrifuge within 2 hours at 1000-1300g for 10 minutes at room temperature.
3. Aliquot into two 2 mL labeled cryovials.
4. Store samples at -65°C to -85°C.
5. Ship samples monthly to The Forsyth Institute:

The Forsyth Institute
c/o [name], MS
The Forsyth Institute
[name]
[name]

6.1.9.6 Flow Cytometry Analysis

Blood samples will be collected in one purple and black speckled Cyto-Chex tube (approximately 5 mL) prior to study treatment at screening (may be collected at the same time as blood drawn for routine laboratory tests) and at the time of surgery.

Samples should be processed the day of collection according to the instructions provided below:

1. Fill Cyto-Chex tube completely.
2. Immediately after collection, invert gently 10 times to ensure proper mixing.
3. Do **NOT** centrifuge. Do **NOT** open tube.
4. Ship ambient with Gel packs on the day of collection to Primity Bio:

Primity Bio
C/O [name]
[name]
[name]
USA

5. Email package tracking information to: [contact]

If patients later decide they do not want their specimens collected to be used for future research, they may tell this to the local site principal investigator, who will inform the Study Chair [name]. [name] will use his best efforts to stop any additional studies and to destroy the specimens. Samples stored in the Biorepository will be destroyed; for samples that have been disseminated outside of the Biorepository, [name] will contact the recipient to notify them of the need to halt further research and destroy specimens.

6.2 Screening/Baseline Procedures

Assessments performed exclusively to determine eligibility for this study will be done only after obtaining informed consent. Assessments performed for clinical indications (not exclusively to determine study eligibility) may be used for baseline values even if the studies were done before informed consent was obtained.

All screening procedures must be performed within 7 days prior to registration unless otherwise stated. The screening procedures include:

- Written informed consent (*within 28 days*).
- Review of inclusion and exclusion criteria.
- Complete medical/oncology history.
- Demographics.
- Documentation of concomitant medications.
- Complete physical examination, including vital signs and height.
- Performance status assessment.
- Laboratory tests (*within 7 days; pregnancy test within 72 hours*).
- Blood collection for correlative studies.
- Documentation of tumor staging.
- Tumor biopsy tissue collection for correlative studies (*within 28 days*).

7.0 ADVERSE EVENTS

An adverse event (AE) is any untoward medical occurrence in a patient receiving study treatment and which does not necessarily have a causal relationship with this treatment. An AE can therefore be any unfavorable and unintended sign (including a clinically significant abnormal laboratory finding), symptom, or disease temporally associated with the use of an experimental intervention, whether or not related to the intervention.

Progression of the cancer under study or events which are unequivocally due to disease progression should not be reported as an AE during the study (unless it is considered to be drug related by the investigator).

7.1 Adverse Event Monitoring

Adverse event data collection and reporting, which are required as part of every clinical trial, are done to ensure the safety of subjects enrolled in the studies as well as those who will enroll in future studies using similar agents. Adverse events are reported in a routine manner at scheduled times during a trial. Additionally, certain adverse events must be reported in an expedited manner to allow for optimal monitoring of patient safety and care.

As far as possible, each adverse event should be evaluated to determine:

- duration (start and end dates)
- severity (grade)
- seriousness
- relationship to study agent
- action taken (i.e., none, study agent modification, medical intervention)
- outcome (i.e., resolved without sequelae, resolved with sequelae, ongoing)

Adverse events monitoring begins at the time of initiating study treatment through **90 days** following the last administration of study treatment or study discontinuation/termination, or the initiation of new anti-cancer therapy, whichever is earlier, whether or not related to IPI-549.

Note: Serious adverse events must be recorded in the case report forms for this 90 day-period; however, non-serious adverse events need only be recorded through 28 days post last study drug administration.

All patients experiencing an adverse event at least possibly related to study treatment will be monitored until:

- the adverse event resolves or the symptoms or signs that constitute the adverse event return to baseline;
- any clinically significant abnormal laboratory values have returned to baseline;
- there is a satisfactory explanation other than the study drug for the changes observed; or
- death.

7.2 Severity

All non-hematologic adverse events will be graded according to the NCI Common Terminology Criteria for Adverse Events (CTCAE) version 5.0. The CTCAE v5.0 is available at <http://ctep.cancer.gov/reporting/ctc.html>

If no CTCAE grading is available, the severity of an AE is graded as follows:

Mild (grade 1): Mild; asymptomatic or mild symptoms; clinical or diagnostic observations only; intervention not indicated.

Moderate (grade 2): Moderate; minimal, local or noninvasive intervention indicated; limiting age- appropriate instrumental activities of daily living (ADL). Instrumental ADL

refer to preparing meals, shopping for groceries or clothes, using the telephone, managing money, etc.

Severe (grade 3): Severe or medically significant but not immediately life-threatening; hospitalization or prolongation of hospitalization indicated; disabling; limiting self-care ADL. Self-care ADL refer to bathing, dressing and undressing, feeding self, using the toilet, taking medications, and not bedridden

Life-threatening (grade 4): Life-threatening consequences; urgent intervention indicated.

Fatal (grade 5): Death related to AE.

7.3 Seriousness

A “serious” adverse event is defined in regulatory terminology as any untoward medical occurrence that:

1. Results in death.

2. Is life-threatening.

The patient was at risk of death at the time of the event; it does not refer to an event that hypothetically might have caused death if it were more severe.

3. Requires in-patient hospitalization or prolongation of existing hospitalization.

Note: The following hospitalizations are not considered SAEs:

- A visit to the emergency room or other hospital department < 24 hours that does not result in admission (unless considered an important medical or life-threatening event)
- Elective surgery, planned prior to signing consent
- Admissions as per protocol for a planned medical/surgical procedure
- Routine health assessment requiring admission for baseline/trending of health status (e.g., routine colonoscopy)
- Medical/surgical admission other than to remedy ill health and planned prior to entry into the study. Appropriate documentation is required in these cases.
- Admission encountered for another life circumstance that carries no bearing on health status and requires no medical/surgical intervention (eg, lack of housing, economic inadequacy, caregiver respite, family circumstances, administrative reason).
- Admission for administration of anticancer therapy in the absence of any other SAEs.

4. Results in persistent or significant disability or incapacity.

5. Is a congenital anomaly/birth defect

6. Is an important medical event

Any event that does not meet the above criteria, but that in the judgment of the investigator jeopardizes the patient, may be considered for reporting as a serious adverse event. The event may require medical or surgical intervention to prevent one of the outcomes listed in the definition of “Serious Adverse Event”.

For example: allergic bronchospasm requiring intensive treatment in an emergency room

or at home; convulsions that may not result in hospitalization; development of drug abuse or drug dependency.

7.4 Relationship

Attribution categories for adverse events in relationship to protocol therapy are as follows:

Definite – The AE is *clearly related* to the study treatment.

Probable – The AE is *likely related* to the study treatment.

Possible – The AE *may be related* to the study treatment.

Unlikely – The AE is *doubtfully related* to the study treatment.

Unrelated – The AE is *clearly NOT related* to the study treatment.

7.5 Prior experience

Expected events are those that have been previously identified as resulting from administration of the agent. An adverse event is considered unexpected, for expedited reporting purposes only, when either the type of event or the severity of the event is not listed in the current known adverse events listed in the agent clinical experience section of this protocol or the current Investigator's Brochure.

7.6 Reporting Requirements for Adverse Events

Serious adverse events, or a follow up to a serious adverse event, including death due to any cause other than progression of the cancer under study that occurs to any subject from the time study treatment initiation through 90 days following cessation of treatment, or the initiation of new anti-cancer therapy, requires expedited reporting as described below.

7.6.1 Expedited Reporting

- A. The Study Chair and Site Principal Investigator must be notified within 24 hours of learning of any serious adverse events (SAEs) regardless of attribution, occurring during the study or within 30 days of the last administration of the study drug.
- B. The **UCSD Human Research Protections Program (HRPP) and Moores Cancer Center Data and Safety Monitoring Board (DSMB)** must be notified within 10 business days of “any unanticipated problems involving risk to subjects or others” (UPR).

The following events meet the definition of UPR:

1. Any serious event (injuries, side effects, deaths or other problems), which in the opinion of the Principal Investigator was unanticipated, involved risk to subjects or others, and was possibly related to the research procedures.
2. Any serious accidental or unintentional change to the IRB-approved protocol that alters the level of risk.
3. Any deviation from the protocol taken without prior IRB review to eliminate apparent immediate hazard to a research subject.
4. Any new information (e.g., publication, safety monitoring report, updated sponsor safety report), interim result or other finding that indicates an unexpected change

to the risk/benefit ratio for the research.

5. Any breach in confidentiality that may involve risk to the subject or others.
6. Any complaint of a subject that indicates an unanticipated risk or that cannot be resolved by the Principal Investigator.

C. The **FDA** must be notified by the Study Chair according to the following timelines:

- within 7 calendar days of any unexpected fatal or life-threatening adverse event with possible relationship to study drug, and
- within 15 calendar days of any event that is considered: 1) serious, 2) unexpected, and 3) at least possibly related to study participation.

7.6.2 Routine Reporting Requirements

- A. The **UCSD HRPP** must be notified of any adverse events that are not unanticipated problems involving risk to subjects or others (non-UPRs) at the time of the annual Continuing Review.
- B. The **FDA** must be notified by the Study Chair of all non-serious adverse events annually at the time of the annual report.

8.0 AGENT INFORMATION

8.1 Agent IPI-549

Please refer to Investigator's Brochure for more comprehensive information.

Mechanism of action (or Product description):

IPI-549 drug substance is a freebase, white-to-yellow solid. The IPI-549 drug product is formulated in 2 different capsule strengths (5 mg and 30 mg) for oral delivery with excipients (diluent, disintegrant, and lubricant) that are listed in the FDA Inactive Ingredients Database for approved drug products and/or Generally Regarded as Safe.

Availability: Provided by Infinity Pharmaceuticals Inc.

How supplied: IPI-549 is administered as an oral capsule supplied at the dose specified per subject and/or cohort.

Route of administration for this study: IPI-549 should be self-administered orally (approximately every 24 hours). IPI-549 should be swallowed whole with a glass of water (approximately 8 ounces or 240 mL). Subjects must avoid grapefruit and grapefruit juice while on study drug. Subjects should be advised to avoid food and liquids other than water from 2 hours prior to dosing until 1 hour after dosing.

Side effects:

Adverse Reactions Based on Clinical Data

The following side effects have been observed in 12 people who received IPI-549 according to the results from a Phase 1/1b first-in-human, dose escalation study to evaluate the safety tolerability, pharmacokinetics, and pharmacodynamics of IPI-549 monotherapy and in combination with nivolumab in subjects with advanced solid tumors.

Grade 3 or higher TEAEs occurred in 5 (41.7%) subjects (1 each in the 10,15, and 20mg groups and 2 in the 30mg group.) There was 1 occurrence of each of the following Grade 3 or higher TEAEs: anaemia, haematochezia, small intestinal obstruction, pneumonia, lymphocyte count decreased, and malignant neoplasm progression.

Treatment-emergent SAEs occurred in 5 (41.7%) subjects. Each subject had 1 SAE as follows: malignant neoplasm progression (15mg), haematochezia (20mg), peritonitis (20mg), small intestinal obstruction (30mg), and pneumonia (30mg).

The following side effects have been observed in 56 people who received IPI-549.

Blood and lymphatic system disorders:

Anemia

Gastrointestinal Disorders:

Diarrhea

Nausea

Vomiting

Abdominal pain

General disorders and administration site conditions:

Fatigue

Fever

Local swelling

Metabolism and nutrition Disorders:

Hypomagnesaemia

Nervous system disorders:

Headache

Vascular disorders

Hypertension

Skin and subcutaneous tissue disorders:

Rash

Itchiness

Dermatitis acneiform

Investigations:

Increased liver enzymes
White blood cell count decreased
Blood bilirubin increased

Respiratory, thoracic and mediastinal disorders:

Shortness of breath
Pleuritic pain

9.0 STATISTICAL CONSIDERATIONS

9.1 Study populations

The efficacy population will consist of all subjects who have received 2 weeks of study drug. Any subject who has not received 2 weeks of study drug will be replaced.

The safety population will consist of all subjects who have received any dose of study drug.

9.2 Study Design/Study Endpoints

We anticipate enrolling 15 subjects. The primary analysis will use the efficacy population. Within subject change from the post-treatment to the pre-treatment sample in the immune activation signature will be the primary endpoint. We will test the hypothesis of an increase in this signature using a one sided paired t-test at 5% significance level. With 15 subjects we have 80% power to detect a difference in the mean signature equal to 0.68 standard deviations, which is a modest effect size. Although we lack preliminary data on the magnitude of the standard deviation of within subject changes, effect sizes less than this would be unlikely to be clinically interesting. Also, the differences seen between the poor prognosis and good prognosis groups in Kaneda et al. [2] were greater than this minimal effect size. Thus the study appears to be well-powered to detect meaningful differences.

[figure not shown]

Figure 1: Illustration of shift in the signature distribution, which would yield an effect size of 0.68

9.3 Sample Size and Accrual

We anticipate enrolling 15 subjects. Subjects who do not complete 2 weeks of IPI-549 therapy will be replaced. Thus far, IPI-549 in advanced cancer patients has been well tolerated without serious toxicity. Therefore, we anticipate being able to fully accrue this trial within one year of activation and the administration of IPI-549 will not interfere with planned surgery. If at any time 3 or more subjects have observed progression prior to the start of definitive treatment the study will be halted.

Accrual Targets			
Ethnic Category	Sex/Gender		
	Females	Males	Total
Hispanic or Latino	1	2	3
Not Hispanic or Latino	4	8	12
Ethnic Category: Total of all subjects	(A1)	(B1)	(C1)
Racial Category			
American Indian or Alaskan Native	0	0	0
Asian	1	1	2
Black or African American	1	1	2
Native Hawaiian or other Pacific Islander	0	0	0
White	3	8	11
Racial Category: Total of all subjects	(A2)	(B2)	(C2)

(A1 = A2) (B1 = B2) (C1 = C2)

9.4 Safety stopping rule

The study will be stopped early in the event of excessive toxicity leading to delays in definitive surgery. In particular any grade 3 toxicity will result in discontinuation of IPI-549, and any subject who has not received 2 weeks of study drug will be replaced. If at any time 3 or more subjects have observed progression prior to the start of definitive treatment the study will be halted. In addition, if at any time 3 or more subjects have surgery delayed by one week or more because of adverse events at least possibly related to study drug, the study will be halted. These safety stopping rules will be assessed at least bi-annually in a formal safety report.

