5.5 Discontinuation from Study Participation

Patients may be removed from study participation for the following reasons (in addition to those listed for discontinuation of study treatment):

- The patient or legal representative withdraws consent for follow-up;
- The patient is lost to follow-up;
- The patient dies;
- It is the decision of the investigator.

- Severe allergic or anaphylactic reaction to IPI-549
- Disease progression prior to surgery
- Pregnancy
- Severe or life-threatening toxicity

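### Section 9.4 has no written criterion that pauses or halts the study after a drug-related death before surgery; at most such a death is one of the three events its only numbered toxicity halt needs

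*Combined protocol and SAP*

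**What the plan says.** Section 9.4 contains two numbered study-level halts.

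- Progression: "If at any time 3 or more subjects have observed progression prior to the start of definitive treatment the study will be halted".
- Toxicity: the study is halted "if at any time 3 or more subjects have surgery delayed by one week or more because of adverse events at least possibly related" (meaning related to IPI-549).

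The section opens with a general sentence that has no count and is tied to delay: "The study will be stopped early in the event of excessive toxicity leading to delays in definitive surgery". It also says that a grade 3 toxicity stops drug for the subject concerned. The Study Summary and Sections 5.3 and 9.3 repeat the progression halt but not the toxicity halt.

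A death appears elsewhere in two ways. At subject level, Section 5.5 lists "The patient dies" among the reasons for leaving the study, and Section 9.1 adds "Any subject who has not received 2 weeks of study drug will be replaced". Section 9.3 repeats the replacement rule: "Subjects who do not complete 2 weeks of IPI-549 therapy will be replaced".

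At reporting level, Section 7.6.1 says that the Study Chair and site investigator "must be notified within 24 hours of learning of any serious adverse events (SAEs) regardless of attribution". The FDA is told "within 7 calendar days of any unexpected fatal or life-threatening adverse event with possible relationship to study drug". The HRPP and DSMB are told of unanticipated problems, a category that names deaths, within 10 business days. Section 10.4 gives the DSMB oversight of unforeseen toxicities.

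**The concern.** The subjects have previously untreated, resectable disease and are waiting for definitive surgery. They take an investigational drug for two weeks, and the primary endpoint is a gene-expression signature. In that setting a death caused by the drug before surgery is the gravest outcome, and one would expect the stopping rule to deal with it by name.

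The numbered toxicity rule instead counts week-long postponements. Three of those halt the study. One related death does not reach the threshold on any reading, and no other sentence says that enrolment or dosing stops while the death is reviewed. Followed as written, the next subject can be enrolled and started on drug, and if the subject who died had not completed two weeks, a replacement is added. The gap lies in what is counted. Timing is not the problem, because both halts already apply at any time.

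**Working it through.** The plan states no operating characteristics for its stopping rules, so there is no figure of its own to reproduce. The check is first a reading of the text, then an illustration.

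**Step 1: does a single related death before surgery meet any written criterion?**

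| Provision | Level | Effect of one related death before surgery |
|---|---|---|
| 9.4 progression count (3 or more) | study | none; a toxic death is not progression |
| 9.4 delay count (3 or more) | study | unclear; at most 1 of 3 |
| 9.4 opening sentence | study | no count, tied to delay; applies only by judgement |
| 5.3 and 9.4, grade 3 toxicity | subject | stops drug for that subject |
| 5.5, 9.1, 9.3 | subject | removal; replacement if two weeks were not received |
| 7.6.1 | reporting | 24 hours, 7 calendar days, 10 business days |
| 10.4 | oversight | DSMB informed; no pause criterion stated |

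No row gives a definite study-level pause or halt. On timing, 10 business days is about two calendar weeks, as long as one 14-day course. A further subject could therefore start and nearly finish treatment before the DSMB must be told, although the Study Chair would know within 24 hours.

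**Step 2: how often would a single-death pause fire, and how often would a second death follow?**

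Inputs: n = 15 (Section 9.2). The per-subject probability p of a related death before surgery is not in the documents; 1%, 2% and 5% are assumed. Subjects are treated as independent, and no action is taken after a first death.

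- P(at least 1) = 1 − (1 − p)^15
- P(at least 2) = 1 − (1 − p)^15 − 15p(1 − p)^14
- P(at least 3) also subtracts 105p²(1 − p)^13

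| p | P(0) | P(exactly 1) | P(at least 1) | P(at least 2) | P(at least 3) |
|---|---|---|---|---|---|
| 1% | 0.8601 | 0.1303 | 14.0% | 1.0% | 0.04% |
| 2% | 0.7386 | 0.2261 | 26.1% | 3.5% | 0.3% |
| 5% | 0.4633 | 0.3658 | 53.7% | 17.1% | 3.6% |

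For example, at 2%: 1 − 0.7386 = 0.2614, and 1 − 0.7386 − 0.2261 = 0.0353.

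**Step 3: sensitivity to the number treated.** Replacement can take the number treated above 15. With 20 treated (assumed), P(at least 1) is 18%, 33% and 64%, and P(at least 3) is 0.1%, 0.7% and 7.5%. Across this range a count of three would seldom be reached by deaths alone, so putting deaths into that count would not by itself close the gap.

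**The case against.** Four points can be made for the plan as it stands.

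**A fatal event is a delay without end.** Section 7.2 makes death a grade of adverse event, and surgery that never takes place because of a related event can fairly be read as delayed. This stands. A reader might infer from the wording that a related death counts toward no halt at all; the text does not settle that, because the death can be read as adding one to the count. It still leaves the count two short.

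**The opening sentence of 9.4 has no minimum count**, and the numbered delay rule is added to it. A fatal toxicity that prevents surgery could be brought under that sentence after one case. That is a permissible reading, but it depends on someone judging the toxicity excessive and treating the death as a delay. It is discretion, not a criterion.

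**The death would be escalated.** A reader might infer that the plan's whole response is to remove and replace the subject. The documents do not support that: Section 7.6.1 sends the event to the Study Chair, and to the FDA, HRPP and DSMB when its conditions are met. Section 5.5 is a list of reasons for leaving the study, not a safety response. An ad hoc stop could well follow, and how the institutional DSMB acts on such a report is not described here. What remains is that no pause or halt criterion is written.

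**Such a death may be unlikely in a 14-day course.** Section 8.1 reports no death attributed to the drug, and Section 9.3 describes it as well tolerated. Section 8.1 does list serious treatment-emergent events in 5 of 12 subjects, but these were patients with advanced tumours and the events are not stated to be drug-related, so they do not establish a death risk either. The binomial figures must not be read as an estimate of risk; they mainly show how often the proposed pause would fire.

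**Conclusion.** The concern holds in a limited form. The only numbered toxicity halt needs three delayed operations, a related death before surgery is not clearly among the events counted, and one death cannot trigger that halt alone. Reporting and DSMB oversight soften the gap without closing it.

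The conclusion rests on the wording of 9.4 and its neighbouring sections and needs no assumed rate. The figures do: with 15 treated and assumed rates of 1% to 5%, a pause would occur in 14% to 54% of studies. The benefit is bounded by the chance of a second related death, 1.0% to 17.1%, and only if every reporting route led to no action. The primary analysis is unaffected. This is a cheap improvement in subject protection and not a flaw in the study's inference.

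**What to change.** Add one sentence to Section 9.4: *Any death before surgery at least possibly related to study drug pauses enrolment and new dosing when it is reported, pending DSMB review; the DSMB also decides whether subjects already on drug continue.*

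Optionally, clarify that the count of 3 includes surgery not performed, or death before surgery, because of such events. This removes the ambiguity over what counts as a delay, but adds little once a single death pauses the study.

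The cost is one sentence, or two with the clarification. The DSMB is already named in Section 10.4, and the sample size, primary analysis and threshold of 3 stay as they are. The downside is an occasional pause at the frequencies given above, including after a death later judged unrelated. A pause could also postpone dosing for subjects whose surgery is already scheduled, so the review should be prompt.
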